## 6 STUDY INTERVENTION

## 6.1 STUDY INTERVENTION ADMINISTRATION

### 6.1.1 STUDY INTERVENTION DESCRIPTION

**Theoretical Basis for Pathways.** Hope Theory and Hamann's model of lung cancer stigma guide the conceptual foundation of Pathways (Figure 2). Hope theory is recommended as a theory-based approach to goal setting interventions in palliative care. It suggests the disruption cancer causes to goal pursuit can be addressed by setting values-based goals and increasing agency (will to work on goals) and pathways (planning ways to reach goals). In Hamann's model of lung cancer stigma, stigma comprises negative perceptions from others, constrained disclosure, and internalized self-blame, guilt, or shame, with proximal effects of isolation and inhibited disclosure. Hope combats these effects by helping patients build ways and will to work toward values-based goals, ultimately supporting function.

**Pathways Development** was informed by: (a) [name] prior work with 60 stage IV NSCLC patients to establish patient interest in the intervention and modality; (b) [name] prior hope interventions and [name] cancer goal interference study to develop content (c) review of resources (e.g., Lung Cancer Alliance) and approaches for lung cancer stigma and consultation with [name] to develop stigma content; (d) provider input on the intervention concept; and (e) patient feedback on intervention materials and concept. (see Figure 3).

### Figure 3. Completed Stepwise Process to Develop Pathways

#### 1. Identified patient interest and needs 2. Elicited provider input 3. Patients reviewed intervention

[figure not shown]

Table 1. Overview of Intervention Components

Component	IP	IP	P	P	P	Main Purpose
Values Clarification Exercise - Review list of potential values and priorities (e.g., family, spirituality)	X	*	*	*	*	To Increase - Intrinsic motivation to work on goals
Values-Based Goals - Generate list of potential goals aligned with top values and priorities - Select goals to pursue based on importance and desire for progress	X	*	*	*	*	To Increase - Agency, Awareness of important goals still available to pursue
Identify Pathways for Goals - Generate list of all potential ways to pursue top goal, including action that is consistent with the goal and feasible even on high symptom days - Select pathways to use and plan to implement pathways	X	X	X	X	X	To Increase - Pathways thinking - Agency thinking - Goal setting skills (specific, realistic)
Plan Ways around Goal Obstacles, Responding to Blocked Goals		X			X	To Increase - Pathways thinking

 
- Identify potential obstacles to goals (e.g., symptoms, stigma, treatment information or resource needs) and plan (e.g., if [obstacle], then [solution])
 
- Identify new goals to pursue if goal is blocked (i.e., not feasible)
 
					
 
- Agency thinking
 
 
To Reduce- impact of goal blockages
	

Review Past Success, Personal Strengths
 
 
-Identify time when persisted in goal when it was difficult
 
-Identify personal strengths from list of potential characteristics
 
		X			
To Increase
 
 
- Agency thinking
 
	

Stigma Resources (Workbook)
 
 
- Responses: what to do if someone asks you if you smoked; people are distancing themselves or unsure how to act; feelings about lung cancer creating isolation
 
- Lung cancer advocacy resources; Peer support networks
 
	*	*	*	*	
To Reduce
 
 
- Stigma's impact on patient-identified goals
 
	

Symptom Resources (Workbook)
 
 
- Cancer center patient guides for coping with fatigue, dyspnea, and pain
 
- Strategies to communicate symptoms to the oncology team
 
	*	*	*	*	
To Reduce
 
 
- Undermanaged symptom's impact on patient-identified goals
 
	

Documentation of Patient Goals and Obstacles in EHR (as needed)
	X	X	X	X	X	
To Reduce patient goal obstacles

**Note.** IP = in-person session; P = Phone session; X = component is main focus of session; \* = as needed; EHR = electronic health record

**Pathways Content and Procedures.** See Appendix A for a draft of the intervention manual and Appendix B for a draft of patient materials. The ~6-8 week intervention focuses on increasing patient hope, including reducing obstacles to patient goals, through 5 sessions: 2 in-person and 3 phone-based (Table 1 Overview of Intervention Components). The treatment manual is scripted, with scenario guides (e.g., “goal of living long enough to see...”; self-blame as obstacle to goal related to family). To reduce patient burden, in-person sessions align with typical 3-4 week infusion schedules. To increase adherence, the study coordinator will remind them of sessions.

#### 6.1.2 ADMINISTRATION AND/OR DOSING

As described in Table 1, the intervention will be delivered in 5 sessions over approximately 5-8 weeks. Two sessions will be in-person when patients are in clinic; 3 sessions will be delivered on the phone when patients are not in clinic. In-person sessions are expected to take 30-45 minutes; phone sessions are expected to take 15-20 minutes. In-person sessions can be completed via Zoom or phone, if needed. Phone sessions can be delivered in-person, if needed, when patients are in clinic. The interventionist will be a member of the health profession (e.g., training as nurse, nurse navigator, rehabilitation or occupational therapist). A full dose of the intervention will be defined as completing 2 in-person sessions and at least 1 phone session.

#### 6.2 FIDELITY

##### 6.2.1 INTERVENTIONIST TRAINING AND TRACKING

Interventionist training and fidelity monitoring will follow guidelines of the Fidelity Workgroup of the Behavior Change Consortium. Multiple interventionists will be trained in case of interventionist attrition. [name] (PI) and the study team will conduct an in-person training with review of procedures, treatment manual, and role plays. To minimize drift and evaluate fidelity, the interventionist will audiorecord all sessions and complete fidelity self-checklists each session (topics covered, session duration, and proscribed behaviors; Appendix E). [name] and the study team will review recordings to rate fidelity (topics, length, interventionist competence; Appendix F).

For Phase I, which is intended to inform refinements needed to the treatment manual or fidelity forms, the study interventionist will have regular (e.g., every week a patient is seen) supervision with [name], and [name] and the study team will review all recorded intervention sessions. For Phase II, the single arm feasibility test of the refined intervention, the study interventionist will have regular (e.g., every week a patient is seen) supervision with [name]. To determine if remedial training is needed (fidelity <80%), the study team will review all sessions for the first 10 patients. Two members of study team will randomly select 10% of remaining sessions and rate fidelity.

### 6.3 MEASURES TO MINIMIZE BIAS: RANDOMIZATION AND BLINDING

This is a single arm intervention design. To help minimize bias, the study coordinator, not the interventionist, will collect patient-reported data and data from the electronic health record related to referrals that could be associated with the intervention.

### 6.4 STUDY INTERVENTION

Treatment adherence will be defined by patient participation (“yes/no” to whether a patient was present and agreed to participate in the session) in at least 3 of 5 intervention visits. We will also track engagement through study interventionist ratings of patient engagement in each session (Appendix G).

Treatment receipt will be assessed through patient ratings of components received and non-specific factors after in-person session 1 and post-intervention with the coordinator and a pre-posttest goal setting exercise (Appendix H).

Treatment enactment will be assessed from review of recordings for demonstration of skills.

### 6.5 CONCOMITANT THERAPY

Patients will be able to receive concomitant treatment while on study. This may include counseling, palliative care, complementary and alternative therapies, psychotropic medications, and rehabilitation. Indeed, one of the anticipated effects of the intervention is a facilitated referral to supportive services. We will track concomitant treatment use through review of

electronic health record for services used during the study intervention period as well as by asking patients at follow-up whether they engaged services while completing the intervention.

## 7 STUDY INTERVENTION DISCONTINUATION AND PARTICIPANT DISCONTINUATION/WITHDRAWAL

### 7.1 DISCONTINUATION OF STUDY INTERVENTION

If a patient discontinues the intervention, but not the study, remaining study procedures will be completed (e.g., post-assessment). Patients who discontinue the intervention will be asked to indicate the reason why they are discontinuing (e.g., intervention burden, decline in functional status, etc.; Appendix I). If a patient's post-assessment is due to be completed within 2 weeks of discontinuing the intervention, the post will be administered at the time of discontinuation. If the post assessment is scheduled for more than 2 weeks from the date they discontinue the intervention, the post assessment will be administered at the originally scheduled assessment.

Patients may be discontinued from the intervention by the investigative team if the study team or treating physician has concerns about the patient's mental status or psychological wellbeing, at which point procedures for managing patient safety and evaluating adverse events will be followed. The study will document reasons for discontinuing a patient (Appendix I).

### 7.2 PATIENT DISCONTINUATION/WITHDRAWAL FROM THE STUDY

Participants are free to withdraw from participation in the study at any time upon request.

An investigator may discontinue a participant from the study for the following reasons:

- Significant study intervention non-compliance
- Lost-to-follow up; unable to contact subject (see Section 7.3, Lost to Follow-Up)
- Any event or medical condition or situation occurs such that continued collection of follow-up study data would not be in the best interest of the participant (Note: patients who are hospitalized during the study period will be offered the opportunity to continue the intervention in the hospital or resume upon discharge. Patients who become hospitalized and elect to discontinue the intervention will still have option to continue the study to complete assessments).
- The participant meets an exclusion criterion (either newly developed [e.g., change in mental status] or not previously recognized) that precludes further study participation.

The reason for participant discontinuation or withdrawal from the study will be recorded (Appendix I). Patients who sign the informed consent form but do not receive the study intervention may be replaced. Patients who sign the informed consent form and receive the

study intervention and subsequently withdraw, or are discontinued from the study, will not be replaced.

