#### 9.4.2 ANALYSIS OF THE PRIMARY ENDPOINT(S)

The primary outcome of the feasibility is enrollment ( $\geq 60\%$ ). A one-sample binomial test will be used to compare the observed enrollment percentage to 60%.

Enrollment (primary): Number of patients enrolled divided by the number of eligible patients approached

Retention: The percentage of patients who complete baseline and post-treatment questionnaires

Adherence: The percentage of patients who complete at least 3 of 5 sessions in 10 weeks.

Acceptability: Mean post-treatment patient ratings  $\geq 7/10$  on intervention satisfaction (primary), convenience, helpfulness, relevance, recommendation to others, worth doing (0 = not at all to 10 = extremely); and a brief semi-structured interview to explore factors associated with acceptability

---

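### Section 7.2 lets investigators end study participation for undefined intervention non-compliance, so retention can depend on adherence and post-treatment data can come from a selected group

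*Combined protocol and SAP*

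**What the plan says.** Protocol section 7.2 opens its list with "An investigator may discontinue a participant from the study for the following reasons". The first reason is "Significant study intervention non-compliance", without a definition of what is significant. Loss to follow-up is a separate reason. A further reason refers to situations in which "continued collection of follow-up study data would not be in the best interest of the participant", so leaving the study is understood to end follow-up. Patients who received the "study intervention and subsequently withdraw, or are discontinued from the study, will not be replaced".

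Section 7.1 deals with stopping the sessions only: "If a patient discontinues the intervention, but not the study, remaining study procedures will be completed". It then sets the timing of the post-assessment for these patients.

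Section 9.4.2, repeated in the appended Analysis Plan, defines retention as "The percentage of patients who complete baseline and post-treatment questionnaires". It defines adherence separately, as at least 3 of 5 sessions within 10 weeks. Section 3 sets a threshold of 70% for each. Neither document gives the retention denominator or says how patients removed by an investigator are counted.

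**The concern.** A patient who skips sessions but can be reached can be handled in two ways. Under section 7.1 the patient stays due for the post-assessment. Under section 7.2 the investigator may end participation and the post-assessment is never requested. No text says which section applies, so an undefined judgment can decide whether the patient has the chance to be retained.

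Three results are exposed:

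- **Retention.** It is meant to show whether patients stay in the study, separately from whether they attend sessions. Removal for poor attendance merges the two.
- **Acceptability.** The ratings are taken after treatment, and section 8.1 plans an exit interview for every Phase II patient. Patients who engaged least may have the most to say about burden or relevance.
- **Pre-post change.** Section 9.4.3 says the main purpose is to estimate standard deviations for future studies. These would come from the better attenders.

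**Working it through.** **The plan's own retention figures.** Section 9.2 takes 40 patients and a true retention of 60%, and doubts feasibility if more than 21 are not retained, that is, if 18 or fewer are retained. The exact binomial gives P(X ≤ 18 | 40, 0.60) = 0.039, so the operative rule reproduces at below 0.05. (The parenthesis in that section uses 19 or fewer, which gives 0.074; that is a separate matter.) The entry for version 7 in the Amendment History expects 55 enrolled to yield 40 evaluable cases: 40/55 = 72.7%.

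**Which patients the clause reaches.** Unreachable patients already have their own ground in sections 7.2 and 7.3. The non-compliance ground therefore mainly adds patients who can still be contacted. Section 8.1 allows questionnaires on paper, online or by phone, so missing sessions does not in itself prevent a post-assessment.

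**Effect on retention.** Let A be adherence, rA the post-assessment completion among adherers and rN that among non-adherers. With all 55 patients in the denominator,

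retention = A × rA + (1 − A) × rN.

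Removing every non-adherer sets rN = 0, and retention = A × rA cannot then exceed adherence. The 70% threshold needs 0.70 × 55 = 38.5, so 39 patients. The documents give neither rA nor rN. The table assumes rA = 90% and compares full removal (rN = 0) with half of the non-adherers completing the post-assessment (rN = 50%). The last column is the binomial probability of at least 39 of 55.

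| A | rN | Retention | Expected retained of 55 | P(≥ 39) |
|---|---|---|---|---|
| 70% | 0 | 0.70 × 0.90 = 63% | 34.65 | 0.14 |
| 70% | 50% | 0.63 + 0.30 × 0.50 = 78% | 42.9 | 0.92 |
| 80% | 0 | 0.80 × 0.90 = 72% | 39.6 | 0.64 |
| 80% | 50% | 0.72 + 0.20 × 0.50 = 82% | 45.1 | 0.99 |
| 90% | 0 | 0.90 × 0.90 = 81% | 44.55 | 0.98 |
| 90% | 50% | 0.81 + 0.10 × 0.50 = 86% | 47.3 | > 0.99 |

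Full removal is the extreme; partial use of the clause falls between the two rows of each pair. Each removed patient who would have completed the post-assessment costs 1/55 = 1.8 percentage points.

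**Other denominator.** If removed patients are left out altogether, full removal gives retention = rA = 90% whatever the adherence. The same decision can therefore move the criterion down or up.

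**Effect on pre-post change.** Suppose mean change is better by d in adherers than in non-adherers. The share of adherers among patients with post data is w = A × rA / (A × rA + (1 − A) × rN), and the complete-case mean is too favourable by (w − A) × d. At A = 70% and rA = 90%, with d assumed to be 0.25 to 0.5 SD:

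- rN = 0: w = 1, so 0.30 × d = 0.075 to 0.15 SD.
- rN = 50%: w = 0.63/0.78 = 0.808, so 0.108 × d = 0.027 to 0.054 SD.

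**The case against.** A reader might infer that sections 7.1 and 7.2 contradict each other. They do not. Section 7.1 is conditional on the patient staying in the study and section 7.2 covers leaving it, so both can be followed. The defect is that a poor attender is assigned to neither.

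A reader might also infer that data are thrown away. No text deletes anything already collected; later assessments are simply not obtained, and only if a discretionary power is used. The documents do not show that it was used for non-compliance. The Amendment History mentions patients who had to be discontinued but gives no reasons.

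Nor can a loss be sized by subtracting removed patients from the forecast of 40 of 55. That forecast already allows for attrition and discontinuations, so the subtraction would count them twice. Sampling error is also wide: the exact 95% interval for 40/55 is 59.0% to 83.9%.

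There are real mitigations. Reasons for discontinuation are recorded, section 7.3 requires efforts to contact and reschedule, hospitalized patients keep the option of completing assessments, and section 9.4.1 compares drop-outs and low attenders on demographic, clinical and baseline data. These make selection visible but do not recover missing post-treatment scores or ratings. The pre-post analysis is descriptive, which limits the harm there.

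What stands is that an undefined, discretionary ground can end data collection from patients who could still supply it, and that it bears on a stated feasibility criterion.

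**Conclusion.** The point holds as an avoidable source of selection and of overlap between two criteria meant to be separate. Its size depends on how often the clause is used, which is unknown, and on completion rates that the documents do not give. Under the assumed 90% completion among adherers, full removal against 50% completion among non-adherers changes the chance of reaching 39 of 55 from 0.92 to 0.14 at 70% adherence. At 90% adherence it hardly matters (above 0.99 against 0.98).

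The direction for retention cannot be stated until the denominator is fixed. Upward bias in acceptability and pre-post means is plausible, but it rests on less engaged patients rating lower or changing less, and the documents do not quantify that. The enrollment endpoint is untouched. The change should be made, but the point does not threaten the trial's primary conclusion.

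**What to change.** 1. In section 7.2, delete intervention non-compliance as a ground for ending study participation. These patients then follow the data-collection path of section 7.1 and remain due for the post-assessment unless they withdraw, are lost to follow-up or meet another ground in section 7.2.
2. In section 9.4.2 and the Analysis Plan, compute retention over all Phase II patients who enrolled and started the intervention. This fits the replacement rule in section 7.2, which allows replacement only of patients who consented but did not receive the intervention.
3. Reconcile the related text. Section 4.4 makes study completion depend on at least 3 sessions, and section 7.3 lets staff judge whether a patient who misses visits should continue in the study. Both should be consistent with sections 7.1, 7.2 and 9.4.2, so that attendance alone does not decide who is followed up or counted as retained.

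The cost is one deleted line, a denominator sentence, matching edits and a few more post-assessments, which the Schedule of Activities already plans for enrolled patients. Some low attenders will still not respond; they then count as not retained, which is what the criterion should record.

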## 9.2 SAMPLE SIZE DETERMINATION

The target sample of 6 patients for Phase I is based on the aim of refining procedures and content. We anticipate that 6 will be sufficient given that we have already had patients review proposed intervention materials to provide feedback and initial refinement.

The target sample size of 40 evaluable cases for Phase II is based on the goal of estimating the probabilities and means for 3 feasibility outcome measures (enrollment  $\geq$  60% [primary], retention  $\geq$  70%, adherence [defined as completing at least 3/5 sessions]  $\geq$  70%). We will use feasibility outcomes to inform an efficacy trial. Here we present some basic power calculations for the above 3 outcomes. Assuming a negative binomial distribution and true probability of enrollment of 60%, the probability that we would have to approach 55 or more people to recruit 40 is  $<0.05$ . If we approach  $\geq$  55 patients to enroll 40, it is unlikely the true probability of enrollment is 60% or greater, concluding a future efficacy study with our criteria may not be feasible. Out of 40 patients, if the true probability of retention is 60% we expect at least 19 patients will be retained (i.e., probability of  $n \leq 19$  retained given true retention probability of 60% is  $<0.05$ ), so if more than 21 patients are not retained, an efficacy study may not be feasible. We have 80% power (using a 2-tailed alpha of 0.05) to detect an adherence proportion of 0.72 if we assume a null hypothesis adherence proportion of 0.50.

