## 9.3 POPULATIONS FOR ANALYSES

The sample from phase I ( $n = 6$ ) will be used to refine procedures and the intervention protocol. The sample from phase II ( $n = 55$ ) will be used to analyze feasibility and acceptability data and describe pre-post changes in patient-reported outcomes.

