## 9.4 STATISTICAL ANALYSES

### 9.4.1 GENERAL APPROACH

For Phase I we will use qualitative methods to analyze patient feedback from the exit interviews and descriptive statistics to summarize participants' acceptability ratings of the intervention. The interviews will be transcribed verbatim and managed in ATLAS.ti or other qualitative software for analysis. The PI and study coordinator will code interviews by domains (e.g., session relevance, delivery mode, ease of participation). Data will be analyzed using thematic content analysis to describe patient perceptions and identify patterns in the patient experience. Quantitative and qualitative findings from Phase I will be synthesized along with interventionist process notes and

included in a report. This report will be used to determine potential refinement in the recruitment procedures, intervention content, intervention delivery, fidelity forms, and retention strategies. The study team will review this report to reach consensus on refinements needed for Phase II testing.

For Phase II, we will use descriptive statistics (means, standard deviations, median, range) to examine the distribution of continuous variables. We will calculate 95% CIs for each of the feasibility measures to determine the range of estimates that are consistent with our data.

We will use one-sample negative binomial probabilities and tests of binomial proportions to compare rates of feasibility to hypothesized values. We will also summarize reasons for patient ineligibility and refusal to participate. In exploratory analyses, we will monitor and compare the patients who drop out or do not complete 3 or more sessions by demographic and clinical characteristics, and baseline scores of the measures (e.g., distress, lung cancer stigma). We will also investigate any differences in patient enrollment, retention, or adherence by treatment type (chemotherapy vs. immunotherapy) to identify an optimal patient population for a future study.

We will calculate inter-rater reliability for fidelity scores between raters of intervention fidelity.

Statistical significance will be indicated by  $p < .05$ .

---

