### **9.4.2 ANALYSIS OF THE PRIMARY ENDPOINT(S)**

The primary outcome of the feasibility is enrollment ( $\geq 60\%$ ). A one-sample binomial test will be used to compare the observed enrollment percentage to 60%.

Enrollment (primary): Number of patients enrolled divided by the number of eligible patients approached

Retention: The percentage of patients who complete baseline and post-treatment questionnaires

Adherence: The percentage of patients who complete at least 3 of 5 sessions in 10 weeks.

Acceptability: Mean post-treatment patient ratings  $\geq 7/10$  on intervention satisfaction (primary), convenience, helpfulness, relevance, recommendation to others, worth doing (0 = not at all to 10 = extremely); and a brief semi-structured interview to explore factors associated with acceptability

---

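### Do consented patients who never start, and may be replaced, fall out of the retention and adherence denominators?

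*Combined protocol and SAP*

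**What the plan says.** Section 7.2 of the protocol treats two groups differently. On those who never start: "Patients who sign the informed consent form but do not receive the study intervention may be replaced". Those who consent and receive the "study intervention and subsequently withdraw, or are discontinued from the study, will not be replaced".

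Section 9.3 says the Phase II sample of 55 "will be used to analyze feasibility and acceptability data and describe pre-post changes in patient-reported outcomes". Section 9.4.2, repeated in the Analysis Plan, gives enrollment an explicit numerator and denominator but defines the other two rates more briefly: "Retention: The percentage of patients who complete baseline and post-treatment questionnaires" and "Adherence: The percentage of patients who complete at least 3 of 5 sessions in 10 weeks". Each has a 70% criterion in the objectives.

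Section 9.2 adds two benchmarks based on 40 patients. For retention: "so if more than 21 patients are not retained, an efficacy study may not be feasible". For adherence: 80% power at a true proportion of 0.72, "if we assume a null hypothesis adherence proportion of 0.50". Section 9.4.1 and the Analysis Plan also promise 95% confidence intervals, binomial tests against hypothesized values, and an exploratory analysis to "compare the patients who drop out or do not complete 3 or more sessions by demographic and clinical characteristics".

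**The concern.** Consent and baseline fall at Visit 1 and the first session at Visit 2, so a patient can consent, complete baseline and never start. Section 5.3 counts consented patients as screen failures only when they are ineligible, so an eligible non-starter is not one. Section 7.2 lets that patient be replaced, and no sentence says whether the replaced patient remains in the two denominators.

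If recruitment ran until 55 patients had started and the replaced ones were dropped, adherence would describe starters only, because a patient with no sessions always fails the three-session requirement. Retention would be affected only for replaced patients with no post-assessment, since Section 7.1 lets a patient who stops the intervention still complete it. Both rates could then exceed what a later trial counting everyone who consents would see, and both belong to the feasibility definition meant to inform that trial. An optional rule with no matching analysis rule also looks like a choice left open until the results are known.

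**Working it through.** **1. The plan's own figure.** For adherence, n = 40, null 0.50, alternative 0.72, two-sided alpha 0.05. The exact binomial test rejects at 13 or fewer or at 27 or more (actual alpha 0.038), with power 0.794. The stated 80% reproduces.

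**2. Who the 55 are.**
- Section 8.1 requires enrollment within 21 days of screening. The Schedule of Activities (Section 1.2) puts the same 21-day limit on Visit 1, where consent is taken. Enrolled therefore means consented.
- The Amendment History (version 7) describes 55 as the number to enroll, expected to yield 40 evaluable cases after attrition and discontinuations. Section 9.3 analyzes that 55.
- Section 6.4 scores adherence yes or no for each patient, so zero sessions scores no.
- Section 7.3 treats a patient who misses three intervention visits and cannot be reached as withdrawn from the study. That gives some non-starters a disposition.
- The exploratory comparison in Section 9.4.1 groups drop-outs with patients below three sessions, and uses baseline scores. A patient with a baseline and no sessions fits that group.

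None of these names a denominator. All point toward keeping non-starters, and nothing says the 55 are starters.

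**3. Size if the 55 were starters.** Let k be the number of replaced eligible non-starters. The documents give no value, so k = 1, 2, 3 is assumed, with no successes among them. The starters-only rate exceeds the all-consented rate by the factor (55 + k)/55 = 1.018, 1.036, 1.055.

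The planning yield is 40/55 = 72.7%.
- If the k are additional to the 15 expected losses (55 − 40): 40/56 = 71.4%, 40/57 = 70.2%, 40/58 = 69.0%.
- If the k are among the 15: all consented stays at 72.7%, and starters only is 40/54 = 74.1%, 40/53 = 75.5%, 40/52 = 76.9%. Every version passes.

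The smallest passing count is 0.70 × (55 + k), rounded up: 39 for k = 0 (38.5), 40 for k = 1 (39.2), 40 for k = 2 (39.9), 41 for k = 3 (40.6). The verdict changes only at exactly 39 successes for k = 1 or 2, and at 39 or 40 for k = 3. With X binomial(55, p), p being the true rate among starters:

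| p | P(X = 39), k = 1 or 2 | P(X = 39 or 40), k = 3 |
|---|---|---|
| 0.65 | 7.6% | 13.3% |
| 0.70 | 11.6% | 22.5% |
| 0.72 | 11.6% | 23.5% |
| 0.75 | 9.3% | 20.4% |
| 0.80 | 3.2% | 8.4% |
| 0.85 | 0.3% | 1.1% |
| 0.90 | <0.1% | <0.1% |

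**4. The planned inference.**
- Wilson 95% interval: 40/55 gives 59.8% to 82.7%; 40/58 gives 56.2% to 79.4%. The largest shift, 72.7 − 69.0 = 3.8 points before rounding, is small beside either width.
- Exact two-sided test against 0.50: 39/55 p = 0.003; 39/58 p = 0.012. Both reject.
- Exact two-sided test against 0.70: 39/55 p = 1.00; 39/56 p = 1.00; 39/57 p = 0.77; 39/58 p = 0.67. None rejects.
- Section 9.2 retention rule: more than 21 of 40 lost is more than 52.5%. Three extra losses give 18 of 58, or 31.0%.

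**The case for a change.** The best case for acting is that the plan does not write the denominator down, a sentence would settle it, and the margin at the planning yield is only 2.7 points. Three additional non-starters take 72.7% to 69.0%; five would give 40/60 = 66.7% and ten 40/65 = 61.5%. If 75% of starters succeed and 90% of those who consent start, the all-consented rate is 0.75 × 0.90 = 67.5%. The chance of observing at least 39 of 55 is then 0.81 when the 55 are starters and 0.35 when they are all consenters.

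The arithmetic is right and the silence is real. The exploratory comparison and the amendment rationale support the inclusive reading without formally defining it. But each of these figures first requires replacement to be used, the 55 to be taken as starters and the replaced patients to be discarded, and the plan directs neither of the last two. The 10% non-start rate is an assumption. The fall to 69.0% also adds losses to the 15, whereas a yield of 40 from 55 enrolled most naturally already contains patients who never started.

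**Conclusion.** No change is needed. This is a definition left unwritten that the rest of the protocol fills sensibly: retention and adherence are taken over the 55 enrolled, that is consented, Phase II patients. A non-starter counts as non-adherent, and as not retained when the post-assessment is missing. Withdrawals are documented from Visit 1, so the number who never started can be reported and a starters-only rate shown, labelled as such, if wanted.

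On the less natural reading, with one to three replaced non-starters, the rates move by at most about 4 points and the 70% verdict changes only at one or two specific counts. A larger number would move the estimates further, but the documents give no rate to suggest it. The conclusion rests on enrollment meaning consent at Visit 1 and on replacement adding a patient without deleting one. The primary enrollment endpoint is untouched, as are the Section 9.2 retention rule and the tests against 0.50 and 0.70 over the range examined.
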